10.4 Treatments

10.4.1 Treatments Administration

Patients will be provided with verbal and written instructions on how to administer the study product at home. At Visit 1, eligible patients will receive a 4 oz (117 g) tube of randomized study product (i.e., Test, Reference or Placebo). Study product should be applied on the day of or the day after enrollment into the study. The day of dosing will be considered Day 1. Patients, infested household members, and/or caregivers will be instructed to apply the study product to dry hair in an amount sufficient (up to 1 tube) to thoroughly coat the hair and scalp, avoiding contact with the eyes. Study product should be left on the scalp for 10 minutes before rinsing with water only. Patients should wash their hands after application of the study product. Hair should be allowed to dry naturally (pat drying with decontaminated towel is permitted) and left uncovered after application of the study product. Following application and rinsing of the study product, patients may not shampoo, wash, or rinse their hair or scalp until the Day 2 visit has been completed.

If any non-infested household member is pregnant or lactating at the time of the study, this person may not be involved with application of the study product to any household members.

The study product should be applied as a single dose. Patients should not use the product more than once. Tubes of study product will be collected at Visit 2 and the site will verify the product was used and rinsed. If a patient inadvertently does not return a tube of study product at its respective return visit, the patient should be instructed to return it as soon as possible or at the next visit.

On Day 1, before applying treatment, all bedding, hats, clothing, and towels used by infested persons or their household, sexual, and close contacts in the two days before treatment should be decontaminated by machine washing in high temperatures (at least 150°F) and drying in a hot dryer for at least 20 minutes (additional time should be added if large loads are dried). Clothing or items that are not washable can be dry-cleaned or sealed in a plastic bag and stored for two weeks. Personal care items such as combs, brushes, and hair clips should be washed in hot water (at least 135°F) for 10 minutes. Instructions on good hygiene and proper methods of decontamination will be provided to the patient and caregivers.

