10.5.1 Visit 1 (Day -1 to 1): Screening/Baseline

1. **Informed Consent:** Patients who are willing to comply with study procedures will read and sign the ICF, as appropriate. Patients who are considered minors will read and sign the assent to participate form, as appropriate, and their parent or legal guardian must sign the ICF. Patient's 11-17 years of age will read and sign an IRB-approved assent form and patients 6-10 years of age will provide verbal assent. Patients 6 months-5 years of age will be exempt from providing assent based on the child's comprehension and cognitive skills. All infested members of a household must agree to receive treatment for anyone in the household to be enrolled.
2. **Medical History and Baseline Demographics:** Review the patient's demographic and medical history.
3. **Concomitant Medication:** Review the patient's use of any medications in the last four weeks.
4. **Vital Signs:** The patient's vital signs will be recorded (pulse, blood pressure, temperature and respiration rate).
5. **Pregnancy Test:** A urine pregnancy test will be required of all female patients of childbearing potential before enrollment.
6. **Louse Examination:** An Investigator or staff member, who is experienced and trained in detection and evaluation of head lice, will perform a visual inspection for the presence of live lice (i.e., live adults and/or nymphs). Louse examination should be conducted for 15 minutes or longer, unless any live lice are detected in less time. Duration of examination and number of live lice should be recorded in the patient's eCRF.
7. **Inclusion/Exclusion Criteria Review:** Study staff will confirm that the patient meets all inclusion/exclusion criteria.
8. **Application Site Reactions:** The Investigator will grade the individual signs and symptoms presented in Appendix A. This will serve as a baseline for subsequent assessments of application site reactions.
9. **Dispense Study Product:** Eligible patients will receive one tube of study product with instructions for dosing at home. Tubes will be dispensed for all members of a patient's household.

CONFIDENTIAL PROTOCOL

A Randomized, Double-Blind, Placebo-Controlled, Parallel-Design, Multiple-Site Clinical Study to Evaluate the Therapeutic Equivalence and Safety of Ivermectin Lotion 0.5% (Actavis Laboratories UT, Inc.) to SKLICE® (ivermectin) Lotion, 0.5% (Arbor Pharmaceuticals, LLC) in the Treatment of Human Head Lice Infestation

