10. **Provide Patient Diary:** A diary will be provided to record date and time of dosing, AEs, including any ocular discomfort, and concomitant medications.

11. **Adverse Events:** Patients will be questioned about any AEs that occurred during the visit.

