10.7.1 Adverse Event Definition

An AE is any untoward medical occurrence in a patient, regardless of whether it has a causal relationship with this treatment.

In this study, any AE occurring after the patient has signed the ICF/assent until the end of follow-up period should be recorded and reported as an AE.

An AE can, therefore, be any unfavorable and unintended physical sign, symptom, or laboratory parameter that develops or worsens in severity during the course of this study, or significant worsening of the disease under study or of any concurrent disease, whether or not considered related to the study product. A new condition or the worsening of a pre-existing condition will be considered an AE. Stable chronic conditions (such as arthritis) that are present before study entry and do not worsen during this study will not be considered AEs.

Accordingly, an AE can include any of the following:

- intercurrent illnesses
- physical injuries
- events possibly related to concomitant medication
- significant worsening (change in nature, severity, or frequency) of the disease under study or other pre-existing conditions drug interactions
- events occurring during diagnostic procedures or during any washout phase of this study
- laboratory or diagnostic test abnormalities that result in the withdrawal of the patient from the study, are associated with clinical signs and symptoms or a serious adverse event (SAE), or require medical treatment or further diagnostic work up, or are considered by the Investigator to be clinically significant (Note: Abnormal laboratory test results at the screening visit that preclude a patient from entering the study or receiving study treatment are not considered AEs.)

A treatment-emergent AE is any AE that occurs after initiation of study product, or any event already present that worsens in either intensity or frequency following exposure to study product.

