11.8 Safety Analysis

Adverse events will be classified using standard Medical Dictionary for Regulatory Activities (MedDRA) terminology Version 20.0 or higher and summarized by treatment group. Summary tables comparing the type, date of onset, date of resolution, incidence, severity, relationship to the study product, action taken, and outcome will be prepared by treatment group. If sufficient data exist, then AE frequencies will be compared among treatments using Fisher's exact test or a similar test. Application site reactions and ocular discomfort will be compared descriptively among treatment groups.

Concomitant medication use during the randomized treatment period will be tabulated by patient.

Signs and symptoms of head lice will not be considered AEs, unless in the Investigator's opinion, they have increased in frequency and/or severity to such an extent that the Investigator/patient considers to be clinically significant.

All patients who received randomized treatment and received study product will be included in the comparative safety analysis.

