6. ANALYSIS POPULATION

Per-Protocol Population (PPP)

The PP population will include all randomized patients who:

- Meet all inclusion and exclusion criteria.
- [REDACTED]
- [REDACTED]
- Have no significant protocol deviations.
- Apply the study product as instructed on Day 1.

STATISTICAL ANALYSIS PLAN

Ivermectin Lotion 0.5%

Protocol / Study No. 71691702

Modified Intent-to-Treat Population (mITT)

The mITT population will include all randomized patients who meet all inclusion/exclusion criteria, apply the study product as instructed, and return for at least one post-baseline evaluation visit.

Safety Population

The Safety population will include all patients who are randomized and received study product.

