8.3.1 Adverse Events

All the adverse events (AEs) reported throughout the study will be coded and classified according to the MedDRA (Medical Dictionary for Regulatory Activities) coding dictionary (Version 20.0 or higher). Each adverse event is to be evaluated for date of start and end, seriousness, severity, causal relationship with the study drugs, action taken and outcome.

The total number and percentage of patients with at least one AEs, discontinued study drug due to AEs, AE severity and AEs related to investigational product, serious AEs and death will be summarized by treatment groups.

A summary table of the number and percent of patients with AEs by system organ class, preferred term, and treatment group will be presented. Each patient will be counted only once within each preferred term.

A frequency summary table of the number of AEs by system organ class, preferred term, severity, and treatment group will be presented. Severity will be classified as “Mild”, “Moderate”, or “Severe”.

Similarly, a frequency summary table of the number of AEs by system organ class, preferred term, and relationship to a study drug, and treatment group will be presented. Relationship to a study drug will be classified as “Related” or “Not Related”.

Adverse event frequencies will be compared between treatments using Fisher’s exact test. If the overall Fisher’s test is statistically significant, a pairwise test will be conducted for Test and Reference to determine if the difference in AEs is related to the active product.

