Excluded from Safety	Total	xxx	xxx	xxx	xxx
	Not randomized or did not receive study product	xxx	xxx	xxx	xxx
mITT Population	Total	xxx	xxx	xxx	xxx
Excluded from mITT	Total	xxx	xxx	xxx	xxx
	Did not dose	xxx	xxx	xxx	xxx
	etc.				
PP Population	Total	xxx	xxx	xxx	xxx
Excluded from Excluded from PPP	Total	xxx	xxx	xxx	xxx
	Restricted Medication	xxx	xxx	xxx	xxx
	etc.				

Test: Ivermectin Lotion, 0.5% (Actavis Laboratories UT, Inc.)

Reference: SKLICE® (ivermectin) Lotion, 0.5% (Arbor Pharmaceuticals, LLC)

Placebo: Placebo (vehicle) lotion (Actavis Laboratories UT, Inc.)

OUTPUT: L:\DEV\917\71691702\SAS\OUT\XXXX

Created on: ddmmmyy hh:mm

Page 1 of N

STATISTICAL ANALYSIS PLAN

Ivermectin Cream 0.5%

Protocol / Study No. 71691702

T16.1.9.3.2 Summary of Patients Included in Analysis Population by Study Center

Site No.	Name	Total Randomized	PP				mITT				Safety			
			Test	Reference	Placebo	Total	Test	Reference	Placebo	Total	Test	Reference	Placebo	Total
XXX	XXXX	XXX	XXX	XXX	XXX	XXX	XXX	XXX	XXX	XXX	XXX	XXX	XXX	XXX

Test: Ivermectin Lotion, 0.5% (Actavis Laboratories UT, Inc.)

Reference: SKLICE® (ivermectin) Lotion, 0.5% (Arbor Pharmaceuticals, LLC)

Placebo: Placebo (vehicle) lotion (Actavis Laboratories UT, Inc.)

OUTPUT: L:\DEV\917\71691702\SAS\OUT\XXXX

Created on: ddmmmyy hh:mm

Page 1 of N

STATISTICAL ANALYSIS PLAN

Ivermectin Cream 0.5%

Protocol / Study No. 71691702

T16.1.9.4 Summary of Demographic Data and Baseline Characteristics (Safety Population)

		Test (N = xxx)	Reference (N = xxx)	Placebo (N = xxx)	P-value
Age (years)	n	xxx	xxx	xxx	x.XXXX
	Mean ± SD	xx.x ± xx.x	xx.x ± xx.x	xx.x ± xx.x	
	Median	xx.x	xx.x	xx.x	
	Range	xx.x – xx.x	xx.x – xx.x	xx.x – xx.x	
Race	White	xxx (xx.x%)	xxx (xx.x%)	xxx (xx.x%)	x.XXXX
	Black/African American	xxx (xx.x%)	xxx (xx.x%)	xxx (xx.x%)	
	Native Hawaiian or other Pacific Islander	xxx (xx.x%)	xxx (xx.x%)	xxx (xx.x%)	
	Asian	xxx (xx.x%)	xxx (xx.x%)	xxx (xx.x%)	
	American Indian or Alaska Native	xxx (xx.x%)	xxx (xx.x%)	xxx (xx.x%)	
	Other	xxx (xx.x%)	xxx (xx.x%)	xxx (xx.x%)	
Gender	Female	xxx (xx.x%)	xxx (xx.x%)	xxx (xx.x%)	x.XXXX
	Male	xxx (xx.x%)	xxx (xx.x%)	xxx (xx.x%)	

N= number of patients in the specific treatment group; n= number of patient with data available; % is based on N

Test: Ivermectin Lotion, 0.5% (Actavis Laboratories UT, Inc.)

Reference: SKLICE® (ivermectin) Lotion, 0.5% (Arbor Pharmaceuticals, LLC)

Placebo: Placebo (vehicle) lotion (Actavis Laboratories UT, Inc.)

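### AE tables count events from before dosing, and the Safety set is not clearly limited to patients who applied the product; both pull the safety comparison slightly toward no difference

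*SAP*

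**What the plan says.** **Who is analysed.** SAP 6 and Protocol 11.3.3 share one definition: "The Safety population will include all patients who are randomized and received study product". The Protocol synopsis applies the same two conditions to the comparative safety analysis. Protocol 11.8 words it differently: "All patients who received randomized treatment and received study product will be included in the comparative safety analysis". SAP 8.3 bases every safety analysis on the Safety population.

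**When product is received and when it is applied.** At Visit 1, "Eligible patients will receive one tube of study product with instructions for dosing at home" (Protocol 10.5.1). Under Protocol 10.4.1, "Study product should be applied on the day of or the day after enrollment into the study".

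**Which events are analysed.** Protocol 10.7.1 and 10.7.7 start AE recording at consent. For Visit 1, Protocol 10.5.1 says: "Patients will be questioned about any AEs that occurred during the visit". SAP 8.3.1 opens with "All the adverse events (AEs) reported throughout the study will be coded and classified" and then describes the summaries and Fisher's exact test with no restriction to events after dosing. Protocol 10.7.1 supplies a restriction that could be used: "A treatment-emergent AE is any AE that occurs after initiation of study product". It also includes an event already present that worsens after exposure. Neither SAP 8.3.1 nor shells T16.1.9.9 to T16.1.9.13 use it.

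**The concern.** Objective 3 is to compare the safety of Test, Reference and Placebo. An event that happens in the clinic before the patient goes home to apply the lotion cannot be caused by it. A patient who never opens the tube has no exposure. Blinded, randomized arms should have similar shares of both, so including them adds noise common to all arms and shrinks any real difference.

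SAP 8.3.1 makes the only named pairwise AE test, Test versus Reference, conditional on a significant overall Fisher test. Shrinkage therefore also makes that second step less likely to be reached.

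**Working it through.** The documents give no AE rate, non-dosing rate or safety power, so there is no stated figure to reproduce. The check is first textual, then illustrative.

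**1. Pre-dose events.** AE recording starts at consent. Visit 1 asks about events during that visit. The tube is dispensed at Visit 1 for use at home. So AEs occurring during Visit 1 are pre-dose by design, and SAP 8.3.1 includes them.

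**2. Undosed patients.** The Visit 1 procedures use *receive* for being handed a tube. The mITT and PP definitions, in the same SAP section, use *apply* when they mean dosing. In shell T16.1.9.3.1 the reason for exclusion from Safety is "Not randomized or did not receive study product", and non-dosing appears as an example reason only under mITT. This favours the tube-in-hand reading. Protocol 11.8 adds receipt of randomized treatment as a separate condition, which can be read as requiring dosing.

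**3. Direction.** Let p_A and p_P be the AE rates on active and Placebo after application, u the share of each arm that never applies the product, and b the share with a pre-dose AE (equal across arms and independent of later events). If undosed patients keep the Placebo rate:

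- active: q_A = 1 − (1 − b)(1 − [(1 − u)p_A + u·p_P])
- Placebo: q_P = 1 − (1 − b)(1 − p_P)
- observed difference: q_A − q_P = (1 − b)(1 − u)(p_A − p_P)

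The difference shrinks by the factor (1 − b)(1 − u). The same factor holds if undosed patients are counted as having no AE.

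**4. Size under assumed rates.** All rates are assumptions. The 126 per arm is 378 ÷ 3, using the Protocol synopsis figure for index patients and an assumed 1:1:1 split, because the allocation is redacted. Power is the exact two-sided Fisher test at 0.05 for active versus Placebo, used only as a yardstick.

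| p_A vs p_P | u | b | Difference (points) | Power |
|---|---|---|---|---|
| 20% vs 8% | 0 | 0 | 12.0 | 74% |
| | 2% | 0 | 12.0 × 0.98 = 11.8 | 73% |
| | 5% | 0 | 12.0 × 0.95 = 11.4 | 70% |
| | 5% | 2% | 12.0 × 0.95 × 0.98 = 11.2 | 64% |
| | 10% | 2% | 12.0 × 0.90 × 0.98 = 10.6 | 59% |
| 10% vs 2% | 0 | 0 | 8.0 | 70% |
| | 5% | 0 | 8.0 × 0.95 = 7.6 | 66% |
| | 0 | 2% | 8.0 × 0.98 = 7.8 | 56% |
| | 5% | 2% | 8.0 × 0.95 × 0.98 = 7.4 | 52% |

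**5. How large b could be.** The larger power losses come from b = 2%, which in the second block equals the whole assumed Placebo rate. The pre-dose window is about a day at most. At a constant daily rate, a 2% Placebo rate spread over about 15 days gives b ≈ 2% ÷ 15 = 0.13%, and the 8.0-point difference becomes 8.0 × 0.9987 = 7.99. If early discontinuation cut follow-up to 5 days (assumed), b ≈ 2% ÷ 5 = 0.4% and the difference is 8.0 × 0.996 = 7.97. On this basis pre-dose events matter little, and the rows with b = 0 are the more realistic guide.

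**The case against.** **The word *received* is undefined, and the shell does not settle it.** This stands. mITT requires application, so non-dosing would be a natural mITT example whichever way Safety is read. The Safety row also names non-randomized patients in a table that starts from randomized patients, which looks like boilerplate. SAP 9 warns that the shells may not reflect every aspect of the study. A reader might infer that undosed patients are definitely kept in the Safety set. The documents support that reading but do not establish it.

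**The effect is small.** This also stands. A reader might assume that 1% to 2% of each arm has a pre-dose AE and, with 6% on active against 2% on Placebo, report that a risk ratio of 3.0 falls to (6 + 1)/(2 + 1) = 2.3 or (6 + 2)/(2 + 2) = 2.0. Those pre-dose rates are large for a window of about a day. At 0.13% the ratio is 6.13/2.13 = 2.9. Adding the same amount to both arms leaves the difference at 4 points, and the SAP plans no AE risk ratio.

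**Equivalence does not depend on AEs.** Correct. A reader might infer that the dilution helps the products pass as equivalent. Protocol 11.6 and SAP 8.2.1 decide equivalence only on the primary efficacy endpoint in the PP population, and there is no AE margin. Protocol 11.8 also makes AE testing conditional on sufficient data.

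**Some separation already exists.** Application site reactions have a Visit 1 baseline and are tabulated by visit, and AE start dates appear in L16.2.7.1. This does not reach the AE counts or the Fisher test.

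**Requiring proof of dosing could remove exposed patients.** Someone who dosed at home, had an AE and never came back would have no diary, Visit 2 discussion or returned tube. This is a sound objection to a strict applied-product rule, and the fix has to answer it.

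**Conclusion.** The point holds as a modest defect in the safety analysis. The AE part is clear from the text: the Protocol defines a treatment-emergent AE, and the SAP counts and tests all AEs from consent onward without using it. The Safety-set part is an ambiguity: the definition in SAP 6 and Protocol 11.3.3 can be read to include undosed patients, and Protocol 11.8 does not match it.

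If non-dosing and pre-dose events are similar across arms, both features pull the AE comparison toward no difference. The size is unknown. With 2% to 5% undosed and few pre-dose events, an assumed 12.0-point difference becomes 11.8 to 11.4 points and the illustrative power falls from 74% to between 73% and 70%. Real arms will exceed 126 if non-index patients enrol, since they also belong to the Safety set, so these powers are not forecasts. The equivalence decision is unaffected.

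**What to change.** **AE analysis.** In SAP 8.3.1 and T16.1.9.9 to T16.1.9.13, summarize treatment-emergent AEs as Protocol 10.7.1 defines them, and apply Fisher's test to them in T16.1.9.10. Derive the flag from the diary's dosing date and time (Protocol 10.4.6) and the AE onset date and time recorded in source (Protocol 10.7.7). Treat an AE as treatment-emergent unless the records show that it began before application and did not worsen afterwards. List pre-dose AEs separately.

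**Safety set.** In SAP 6 and Protocol 11.3.3, define it as randomized patients who applied study product. Exclude only those with confirmed non-use from the diary, the Visit 2 discussion or the returned tube, and keep patients whose dosing status is unknown. Add confirmed non-dosing to the Safety exclusion rows of T16.1.9.3.1. Bring Protocol 11.8 and the synopsis into line.

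**Cost.** Wording changes, two derived flags, one rule for unknown dosing or onset times, and slightly smaller denominators. L16.2.7.1 shows AE dates only, so check that onset times reach the database; otherwise the rule for unknown times covers dosing-day events, apart from those reported at the end of Visit 1, which precede home dosing. Make the change before database lock, which is when Protocol 11.1 requires the SAP to be final.

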7. EFFICACY ENDPOINTS

Primary Efficacy Endpoint

The primary efficacy endpoint is the proportion of index patients in each treatment group who are considered a Treatment Success on Day 15 ± 2 . Treatment Success is defined as the absence of live lice.

Secondary Efficacy Variable

The secondary efficacy endpoint is the proportion of all randomized patients (i.e., index + non-index) who are considered a Treatment Success on Day 15 ± 2 . Treatment Success is defined as the absence of live lice.

8. STATISTICAL ANALYSIS METHODS

If not otherwise specified, statistical significance is defined as $p < 0.05$ and is two-tailed. Data will be summarized with respect to demographic and baseline characteristics, efficacy variables and safety variables.

For categorical variables, the number and percent of each category within a parameter will be calculated for non-missing data. For continuous variables, statistics will include number of observations, mean, standard deviation, median, minimum and maximum values.

All statistical analyses will be conducted using SAS[®], Version 9.4 or higher. Datasets will be prepared using headings from Clinical Data Interchange Consortium (CDISC) Study Data Tabulation Model (SDTM) implementation for human clinical trials and ADaM (Analysis Dataset Model). ADaM datasets will include but not limited to ADSL, ADEFF, ADAE, ADVS, ADCM and ADMH.

STATISTICAL ANALYSIS PLAN

Ivermectin Lotion 0.5%

Protocol / Study No. 71691702

8.1 Baseline Characteristics

8.1.1 Baseline Comparability

Baseline characteristics will be evaluated separately for the PP, mITT and Safety populations.

Demographic information collected at baseline includes the following:

- Age (years)
- Gender (Male/Female)
- Ethnicity (Hispanic/non Hispanic)
- Race (White, Black/African American, Native Hawaiian or Other Pacific Islander, Asian, American Indian or Alaska Native, Other)
- Number of live lice

Summary tables by treatment group will be presented. Continuous variables will be summarized using descriptive statistics (number of observations, median, minimum, maximum, mean and standard deviation). Categorical variables will be summarized using frequencies and percentage. Baseline treatment comparisons will be presented using Chi-Square test for the categorical variables, and Analysis of Variance (ANOVA) for the continuous variables.

All data will be listed by treatment and patient.

